7. ASSESSMENT OF SCIENTIFIC OBJECTIVES

7.1. Primary endpoints and outcome measures

- Incidence of adverse events, using the National Cancer Common Terminology Criteria (version 4) up to 12 months following completion of the study treatment. Adverse events

will be summarized by type and severity in tabular format. Fisher's exact test will be used to compare adverse events rates between study arms.

- Composite response rate for metatstatic PCa patients defined as one of the following:
 - A. PSA response rate:
 - 24-week PSA response rate: Patients who achieve at least a 50% reduction in PSA at 24 weeks compared to baseline.
 - Maximal PSA response rate: Patients who achieve at least a 50% reduction in PSA at any time compared to baseline.
 - B. Reduction of circulating tumor DNA following study treatment:
 - 24-week ctDNA response rate: Patients who achieve at least a 50% reduction in ctDNA at 24 weeks compared to baseline.
 - Maximal ctDNA response rate: patients who achieve at least a 50% reduction in ctDNA at any time compared to baseline.
- Changes in ctDNA from pre-treatment (date of screening/randomization) to post-treatment assessments at any time will be evaluated using a paired t-test. ctDNA will be quantified by digital PCR. Changes in ctDNA will be summarized in terms of means and standard deviations.
- For low- and intermediate-risk PCa patients, serum PSA kinetics secondary to study treatment as measured by rate of change before radical prostatectomy. Serum PSA levels will be measured by a standard clinical laboratory test at baseline and at pre-defined timepoints following study treatment as detailed in Appendix 1.

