3. OBJECTIVES

Primary objectives

Low- or intermediate-risk PCa patients:

- To assess safety of the viral vectored ChAd-MVA 5T4 vaccine when administered in combination with anti-PD-1 mAb
- To determine whether ChAd-MVA 5T4 vaccine in combination with anti-PD-1 will impact on the level of PSA in the blood

Metastatic PCa patients:

- To assess safety of the viral vectored ChAd-MVA 5T4 vaccine when administered in combination with anti-PD-1 mAb
- To assess efficacy of the viral vectored ChAd-MVA 5T4 vaccine when administered in combination with anti-PD-1 mAb as measured by composite response rate defined as one of the following:

- reduction of circulating tumour DNA of $\geq 50\%$
- serum PSA decrease of $\geq 50\%$

Secondary objectives

Low- or intermediate-risk PCa patients:

- To assess the magnitude of immune responses in the periphery generated by ChAd-MVA 5T4 vaccine in combination with anti-PD-1 mAb
- To assess immune cell subsets in the prostate secondary to treatment

Metastatic PCa patients:

- To assess the magnitude of immune responses in the periphery generated by ChAd-MVA 5T4 vaccine in combination with anti-PD-1 mAbTo evaluate radiographic progression-free survival at 6 months and one year post enrollment
- To evaluate overall survival at 6 months and one year post enrollment

Exploratory objectives

- To investigate whether ChAd-MVA 5T4 vaccine in combination with checkpoint blockers will lead to up-regulation of PD-L1 expression in the primary tumour or metastatic lesion
- To determine whether ChAd-MVA 5T4 vaccine in combination with PD-1 mAb will impact on the level of PSA-related kallikreins in the blood
- To assess biochemical (PSA) response rates according to PCWG2 criteria
- To assess whether ChAd-MVA 5T4 vaccine administered in combination with anti-PD-1 mAb will lead to reduction of circulating tumour cells
- To evaluate phenotypic and functional profile of immune cells in the blood secondary to treatment
- To evaluate immunologic antigen spreading to other prostate-associated antigens secondary to treatment

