4.3. Allocation to study groups and dosing regime

The 36 subjects will be recruited to the study: 12 patients with low- or intermediate-risk prostate cancer (Group 1) and 24 patients with metastatic prostate cancer (Group 2).

Group 1: Low- or intermediate-risk localised or locally advanced prostate cancer patients scheduled to undergo radical prostatectomy

12 subjects will be treated with ChAd-MVA.5T4 vaccination plus 1 dose of the anti-PD-1 monoclonal antibody Nivolumab

Week 0:	ChAdOx1.5T4	2.5×10^{10} vp	intramuscular injection
Week 1:	MVA.5T4	2×10^8 pfu	intramuscular injection
	Nivolumab	480mg	intravenous infusion

Group 2: Metastatic prostate cancer patients with disease progression on anti-androgen therapy with either enzalutamide or abiraterone

24 subjects will be treated with ChAd-MVA.5T4 vaccination plus 3 doses of the anti-PD-1 monoclonal antibody Nivolumab

Week 0:	ChAdOx1.5T4	2.5×10^{10} vp	intramuscular injection
Week 4:	MVA.5T4	2×10^8 pfu	intramuscular injection
	Nivolumab	480mg	intravenous infusion
Week 8:	Nivolumab	480mg	intravenous infusion
Week 12:	ChAdOx1.5T4	2.5×10^{10} vp	intramuscular injection
	Nivolumab	480mg	intravenous infusion
Week 16:	MVA.5T4	2×10^8 pfu	intramuscular injection

Compliance with Dosing Regimen

Administration of all vaccines and checkpoint inhibitor therapies will be undertaken by a delegated research nurse or investigator in the clinical research facility or oncology treatment suite of the respective study centres. All study treatments will be recorded in the CRF and the relevant accountability log by the research nurse or investigator. There are no self-administered investigational products involved in this study.

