4.4. Duration of study

Subjects undergoing radical prostatectomy will all be followed up for a total duration of 6 months from enrolment. Planned follow up for participants with metastatic prostate cancer is 12 months from enrolment.

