8.5. Reporting procedures

Reporting Procedures for All Adverse Events

After an eligible participant is enroled onto the study on receipt of the first study procedure, all AEs occurred within 28 days of study treatment and only grade 3 AEs outside this time window will be reported in the study case report forms (CRF), whether or not attributed to study procedures. AEs may be observed by the Investigators or reported by the participant either spontaneously or during diary card monitoring. All AEs that result in a subject's withdrawal from the study will be followed up, with their consent until a satisfactory resolution occurs, or until a non-study related causality is assigned.

Reporting Procedures for Serious Adverse Events

All serious adverse events (SAEs) occurring after an eligible participant is enrolled onto the study on receipt of the first study intervention, will be reported throughout the trial period. All SAEs will be documented accurately and notification deadlines respected. SAEs will be reported on an SAE Report Form to the Sponsor or the Sponsor's delegated representative (Chief Investigator) and the Study Medical Monitor (SMM), according to the relevant SOP within 24 hours of the Investigator becoming aware of them. SAEs will not normally be reported immediately to the ethical committee(s) and MHRA unless there is a clinically important increase in occurrence rate, an unexpected outcome, or a new event that is likely to affect safety of trial volunteers, in the opinion of the Chief Investigator and/or SMM. In addition to the expedited reporting above, the Investigator shall include all SAEs in the annual Development Safety Update Report (DSUR) report. Any updates to relevant information concerning the SAE that becomes available after the SAE initial report has been sent (outcome, precise history, results of investigations, copy of hospital report, etc) will be forwarded in a timely manner using the SAE Update Report Form. For all deaths, any available post-mortem reports and relevant medical reports will be made available for reporting to the relevant authorities. The Sponsor, or a medically qualified investigator delegated by the

Sponsor, is responsible for commencing, maintaining and completing the SAE Sponsor Report Form. The anonymity of subjects shall be respected when forwarding this information.

Expectedness

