9. STATISTICS

9.1. Sample size

This is a non-randomised multi-centre phase I/II study. The trial will be open label; given the objective nature of the measurements, this is unlikely to introduce significant bias in assessing key outcomes. Study ID will be assigned to participants in the order in which they are enrolled in the trial. The correspondence between the subject study ID and the treatment number/arm allocation will be noted down in the CRF and subsequently entered in the OpenClinica system.

The total number of subjects enrolled to the study will be 36: 12 subjects with low- or intermediate-risk localised or locally advanced prostate cancer and 24 subjects with metastatic disease.

In this adaptive design study, the sample size of each patient cohort is chosen to allow an initial descriptive report of the safety of the vaccine in combination with checkpoint blockade. In this study, we are targeting a 25% response rate to the vaccine in combination with PD-1 blockade in mCRPC patients. The sample size of 24 patients in Group 2 will require that 6 out of 24 treated patients will have a complete response, partial response or stable disease. The patient cohorts recruited to the KEYNOTE-199 study will serve as a control group for ADVANCE and 11% overall response rate to PD-1 blockade as a monotherapy will be compared with the response rate to the vaccine in combination with anti-PD-1 treatment in the ADVANCE patients.

The 12 patients in the surgical group will be compared for response rate to the 26 surgical subjects treated with the same vectored vaccines but no anti-PD1 in the VANCE trial. None of the 26 patients in VANCE showed a significant reduction in PSA levels during that trial. The

sample size of 12 is chosen to allow an initial descriptive comparison of response rates with and without anti-PD1 to help power any potential future trial.

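### Section 7.1 keeps a Fisher test of adverse-event rates between arms, but the only arms left are two non-randomised cohorts with different dosing, follow-up and capture time

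*Protocol*

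**What the plan says.** Safety is a primary objective in both cohorts (Protocol section 3): "To assess safety of the viral vectored ChAd-MVA 5T4 vaccine when administered in combination with anti-PD-1 mAb". Section 7.1 defines the endpoint as the incidence of adverse events "up to 12 months following completion of the study treatment", to be tabulated by type and severity, and adds: "Fisher's exact test will be used to compare adverse events rates between study arms". No other test is named for adverse events, and no alpha, margin or decision is attached to this one.

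Section 9.1 describes the design: "This is a non-randomised multi-centre phase I/II study". Section 4.3 assigns 12 men to Group 1, with study treatment at weeks 0 and 1. For Group 2 it states that "24 subjects will be treated with ChAd-MVA.5T4 vaccination plus 3 doses of the anti-PD-1 monoclonal antibody Nivolumab", with treatment at weeks 0, 4, 8, 12 and 16. On follow-up, section 4.4 says: "Subjects undergoing radical prostatectomy will all be followed up for a total duration of 6 months from enrolment"; for metastatic patients it gives 12 months.

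Section 8.5 sets what is recorded: "all AEs occurred within 28 days of study treatment and only grade 3 AEs outside this time window will be reported". Serious adverse events are reported throughout the trial.

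**The concern.** With no randomised comparator, a test between arms can only set Group 1 against Group 2. Section 2.2 already uses the word arm for these two groups when it introduces the dosing diagrams. The external comparators in section 9.1 are named for response rate, not for adverse events.

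The two groups differ in almost everything that drives adverse events: disease stage, surgery, number of vaccinations and infusions, length of follow-up, and the time over which low-grade events are written down. Fisher's test on the proportion of men with an event takes none of this into account. A small P value could arise only because Group 2 was observed and dosed for longer, and a reader could take it for a difference in tolerability.

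**Working it through.** The protocol gives no operating figure for this comparison, so there is none to reproduce. The check has two parts.

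**1. Capture time per man**

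- Below grade 3 (28 days from each treatment, section 8.5; dosing weeks from section 4.3). Group 1: last dose at week 1, so 1 + 4 = 5 weeks. Group 2: doses every 4 weeks up to week 16, so the windows join and run to 16 + 4 = 20 weeks. Ratio 20/5 = 4. In total, 12 × 5 = 60 v 24 × 20 = 480 patient-weeks.
- Grade 3 and serious events (whole follow-up). Group 1: last visit at week 24 (Appendix 1). Group 2: 12 months, taken as 52 weeks. Ratio 52/24 = 2.17.
- Dosing visits: 2 v 5. Ratio 2.5.
- Follow-up after the last dose: 24 − 1 = 23 weeks v 52 − 16 = 36 weeks. Neither group reaches the 12 months after treatment named in section 7.1.

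These figures assume that every planned dose is given on schedule.

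**2. How often the test would reject when the underlying risk is equal**

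Assumptions that are not in the protocol: two-sided alpha 0.05, and the same constant hazard per unit (week or dosing visit) in both groups. If p1 is the Group 1 incidence and r the ratio above, the Group 2 incidence is p2 = 1 − (1 − p1)^r. For example, with p1 = 0.20 and r = 4, p2 = 1 − 0.8^4 = 0.59. The rejection probability is the sum, over all outcomes of Binomial(12, p1) and Binomial(24, p2), of the joint probability wherever Fisher's P < 0.05.

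| Group 1 incidence | r = 4 (below grade 3) | r = 2.17 (grade 3, SAE) | r = 2.5 (per dosing visit) | r = 1 (equal window) |
|---|---|---|---|---|
| 2% | 0.1% | 0.1% | 0.1% | 0.1% |
| 10% | 24.6% | 3.1% | 5.4% | 1.6% |
| 20% | 55.7% | 13.7% | 20.9% | 2.5% |
| 30% | 67.6% | 21.1% | 29.8% | 2.7% |

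With r = 4, rejection is 3.4% at 5% incidence. It peaks for mid-range incidences (83% at 50%) and falls again for near-universal events (11% at 90%, 2% at 95%). With equal windows and equal risk it never exceeds 3.0%.

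Equal windows would remove the length artefact but not the differences in disease, surgery and dosing. Power would also be poor: 80% power needs about 10% v 57%, 25% v 77% or 50% v 93%.

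**The case against.** **Stale wording.** The amendment history records that version 3.0 removed the no-vaccine control arm and randomisation. Sections 7.1 and 7.2 still refer to a randomisation date, and section 9.2 to arms within the metastatic cohort. The Fisher sentence is probably another remnant, with no real intention to compare the two cohorts. That stands as the likely origin. It is still the operative text for a primary endpoint.

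**The largest rejection figures are selective.** They need the fourfold ratio, which holds only below grade 3, and a hazard constant in calendar time. Section 4.6.3 says vaccine reactions typically settle within 48-72 hours, so risk may follow doses, and the figures then roughly halve or better. Table 1 puts immune toxicity of grade 3 or above below 2% per organ system, where the test almost never rejects. This stands: 25/56/68% is the upper range.

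**Not strictly a type I error.** Group 2 receives more treatment. A higher incidence per course would be a real difference between regimens, and rejection is an error only against a null of equal risk per week. This also stands. It is why the P value is hard to interpret in either direction.

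**Little depends on it.** A reader might infer that the safety assessment rests on this test, or that a spurious result would carry over to a later regimen. The documents do not support either. Sections 7.1 and 9.2 plan descriptive tables, section 9.1 justifies the sample size as descriptive, and continuation rests on review by the data and safety monitoring committee.

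**Conclusion.** The point holds as a defect in a stated analysis. The only comparison the current text allows is between two non-randomised disease cohorts with unequal dosing, follow-up and capture time, and the named test ignores time at risk. Its P value would not be interpretable as a safety difference.

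That conclusion needs no model; the rejection percentages do. They depend on an assumed alpha, equal constant hazard and full dosing on schedule, and they run from almost zero for rare events up to the fourfold-ratio figures for common low-grade events. A general false-positive rate of 56-68% for adverse events would be an over-reading.

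The practical weight is moderate: the endpoint is co-primary and the sentence is wrong for this design, but the rest of the safety reporting is descriptive and no decision is tied to the test.

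**What to change.** Delete the between-arm Fisher test for adverse events from section 7.1. Report adverse events descriptively for each group, with exact 95% confidence intervals for any-grade, grade 3 or higher and immune-related events, and state the capture window beside each figure.

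If the groups are displayed side by side, do so without a test, over a common window or as exposure-adjusted rates. A 28-day window needs a note that it misses later-onset immune toxicity: the median onsets given in Table 1 run from 1.4 to 3.3 months, so all fall after day 28. A common window also does not make the groups comparable.

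The same pass should check the other leftover references to randomisation and arms in sections 7.1, 7.2 and 9.2. The cost is one sentence in section 7.1 and the table shells. No new data are needed.

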7.2. Secondary endpoints and outcome measures

- Development or increase in anti-5T4 cellular responses following study treatment two weeks post last vaccination and at any time-point on the study. Measurement of T cell responses will be done by IFNy ELISPOT assay to measure T cell responses to tumour and control antigens. Descriptive statistical analysis will be conducted. Immune profile of the prostate (low- or intermediate-risk PCa patients only). Tumour-infiltrating immune cells in surgical specimens and pre-treatment archival diagnostic needle prostate biopsies will be compared. Immune cell density, phenotype and function and will be assessed by immunohistochemistry and digital image analysis of formalin fixed paraffin-embedded tumour tissue samples using a panel of cell surface and intracellular markers. Descriptive statistical analysis will be conducted.
- Radiographic progression-free survival rate as measured by MRI, CT scans or bone scintigraphy (metastatic PCa patients only). Fisher's exact test will be used to compare 6 and 12-month progression-free survival rates between study arms. In order to evaluate progression-free rate as a function of baseline time point, analysis will be conducted using

two different baseline values: date of randomization and one months post last study treatment.

- Overall survival will be assessed for each arm 6 and 12 months post enrolment using the Kaplan-Meier method and log-rank test for statistical significance (metastatic PCa patients only).

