9.2. Analysis

A detailed statistical analysis plan (SAP) will be prepared and finalised with the study statistician before the first interim data analysis.

Data analysis of the following endpoints: safety, efficacy and immunogenicity will be assessed as detailed in Section 7. Safety data will be presented according to frequency, severity and duration of adverse events. Efficacy analysis will be primarily based on evaluation of ctDNA reduction, PSA response rate, radiographic progression-free and overall survival between metastatic PCa study arms. Immunogenicity will consist of descriptive analysis of cellular and humoral immune responses to the vaccine transgene in the circulation, focusing on the magnitude and qualities of T cell responses.

Exploratory analyses may also include, but are not limited to, the analyses described below:
Factors predictive of treatment benefit: baseline demographic, tumour status, haematological or immunological variables may be included as interactions with treatment in logistic, longitudinal or proportional hazards models of efficacy endpoints in order to assess their value as factors predictive of treatment benefit.

Factors predictive of immune response: baseline demographic, tumour status, haematological or immunological variables may be included as explanatory variables in models of qualitative and quantitative immunological endpoints in order to assess their value as factors predictive of immune response.

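### Sections 7.2 and 9.2 order between-arm tests of rPFS and OS, and an rPFS origin at randomisation, in a trial whose only metastatic group is a single non-randomised one

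*Protocol*

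**What the plan says.** **Design.** Section 9.1 states: "This is a non-randomised multi-centre phase I/II study". Section 4.3 defines one metastatic group, Group 2: "24 subjects will be treated with ChAd-MVA.5T4 vaccination plus 3 doses of the anti-PD-1 monoclonal antibody Nivolumab". There is no second metastatic regimen and no allocation step. Section 4.4 adds: "Planned follow up for participants with metastatic prostate cancer is 12 months from enrolment".

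**rPFS (section 7.2, metastatic patients only).** The ordered test is: "Fisher's exact test will be used to compare 6 and 12-month progression-free survival rates between study arms". The rate is to be analysed from "two different baseline values: date of randomization and one months post last study treatment".

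**OS (section 7.2).** It is to be assessed for each arm at 6 and 12 months from enrolment, by the "Kaplan-Meier method and log-rank test for statistical significance (metastatic PCa patients only").

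**Section 9.2.** Efficacy rests mainly on ctDNA reduction, PSA response rate, and "radiographic progression-free and overall survival between metastatic PCa study arms".

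**External control.** Section 9.1 says: "The patient cohorts recruited to the KEYNOTE-199 study will serve as a control group for ADVANCE". It then specifies one comparison, the ADVANCE response rate against 11%. In section 2.2, the text on metastatic patients speaks of efficacy compared with PD-1 inhibition alone and lists PFS and OS among the endpoints.

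**Objectives.** The synopsis and section 3 count rPFS and OS from enrolment. Section 6.1 defines enrolment as receipt of the first ChAdOx1.5T4 vaccination on Day 0.

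**The concern.** Fisher's test and the log-rank test as ordered each compare two samples, and the design supplies one. An origin at randomisation needs a randomisation, and there is none. An analyst following sections 7.2 and 9.2 literally cannot produce these secondary results. Someone must set aside the ordered tests, or bring in a comparator and an origin that the protocol does not define. The trial is open label, so that choice should be written down before outcomes are looked at.

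The second rPFS origin raises a smaller question: whether 12 months of follow-up from enrolment can support a 12-month rate counted from a later start.

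**Working it through.** The protocol gives no power, event count or target for rPFS or OS, so there is no stated figure to reproduce. The check is structural, with some calendar arithmetic.

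**1. Is there a second sample?**
- Metastatic groups in section 4.3: one, n = 24, one regimen.
- Group 1 cannot be the comparator. Section 7.2 limits both endpoints to metastatic patients, and section 9.2 speaks of metastatic arms.
- The Fisher table therefore has an empty second row. For example, 12 progression-free and 12 not, against 0 and 0, gives an undefined odds ratio and P = 1 whatever the split. A log-rank test with one group has nothing to compare.

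**2. Can the external cohort be the second arm?** Section 9.1 specifies only the response-rate comparison. The protocol gives no rPFS or OS figures for that cohort, and a log-rank test would need its individual event times.

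**3. Time origins.**
- Randomisation date: no patient has one.
- Enrolment (Day 0): every patient has one, and the objectives already use it.

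**4. The second rPFS origin, assuming the clock restarts there.** One month = 365.25 / (12 × 7) = 4.35 weeks; 6 months = 26.1; 12 months = 52.2. In section 4.3 the first dose is at week 0 and the last at week 16.

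| | Day 0 dose only | All doses |
|---|---|---|
| Origin | 0 + 4.35 = week 4.3 | 16 + 4.35 = week 20.3 |
| 6-month point | 4.3 + 26.1 = week 30.4 | 20.3 + 26.1 = week 46.4 |
| 12-month point | 4.3 + 52.2 = week 56.5 | 20.3 + 52.2 = week 72.5 |

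Follow-up ends at about week 52, or about week 54 with the 14-day window of the last visit in Appendix 1. Even the earliest 12-month point, week 56.5, lies beyond that. Men still event-free have unknown status at 12 months from this origin. The only men with known status are those who have progressed or died, so a rate among men with known status would be 0% by construction.

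**5. Scans.** Section 6.2 plans imaging at baseline, 6 months and 12 months. For men who complete treatment the origin is week 20.3, and the next scan (week 24 to 26) comes 24 − 20.3 = 3.7 to 26 − 20.3 = 5.7 weeks later. Their 6-month point, week 46.4, has no scan either; the next is at about week 52.

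**6. What a single-group report gives.** Exact (Clopper-Pearson) 95% limits for k of 24 are the 2.5% quantile of Beta(k, 25 − k) and the 97.5% quantile of Beta(k + 1, 24 − k). The protocol assumes no rate, so a range is shown:
- 6/24 = 25%: 10% to 47%
- 12/24 = 50%: 29% to 71%
- 18/24 = 75%: 53% to 90%

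These apply if all 24 men have known status; with censoring, the Kaplan-Meier interval takes their place.

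**The case against.** **The external cohort might be the intended comparator.** Section 9.1 names it as a control group in general terms, and section 2.2 mentions PFS and OS alongside a comparison with PD-1 inhibition alone. So it would be too strong to say that the protocol never contemplates such a comparison. It still does not make that cohort a study arm or supply the data that the ordered tests need. What stands is that section 2.2 should be aligned as well.

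**A reader might infer that the choice will be made after the data are in.** The documents do not support that. Section 9.2 requires an analysis plan finalised before the first interim analysis, and the objectives already fix enrolment as the origin. The plan can settle the matter in time, but the protocol text would still order tests that its design cannot supply.

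**A reader might infer that no man has a 12-month status from the second origin.** That is too absolute: a man who progresses or dies after it has one. Section 7.2 also calls these baseline values, so a changed reference baseline with the same calendar scans is a possible reading. The week figures above depend on the clock restarting.

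**A reader might extend the point to the other Fisher tests.** The between-arm tests of adverse events (section 7.1) and T-cell response (section 7.3) can be run as Group 1 against Group 2, and no decision rule rests on them. They are not part of this defect.

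**Conclusion.** The point holds. Within the current text, sections 4.3 and 9.1 describe one non-randomised metastatic group, while sections 7.2 and 9.2 order comparisons between metastatic arms. The rPFS Fisher test and the OS log-rank test cannot be run within the trial, and one of the two rPFS origins belongs to no patient. This rests on the text alone and needs no numerical assumption.

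The secondary point holds if the clock restarts one month after last treatment: the 12-month rate from that origin cannot be estimated, because its 12-month point lies at about week 56.5 to week 72.5 against follow-up to about week 52.

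The reach is limited. Kaplan-Meier OS from enrolment is sound, and the composite response definition in section 7.1 and the response-rate comparison in section 9.1 are untouched. No sample size or decision rule changes. It should be fixed, as a matter of secondary endpoints.

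**What to change.** **Section 7.2.** Delete the Fisher and log-rank tests. Replace the randomisation date with the date of enrolment (Day 0). Report Group 2 OS by single-arm Kaplan-Meier, and rPFS as 6- and 12-month estimates with 95% confidence intervals from enrolment.

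**Second rPFS origin.** Drop its 12-month rate. If the origin is kept, limit it to a descriptive 6-month landmark estimate among men alive, progression-free and in follow-up at that point. State that for men who complete treatment no scan falls at the origin or at its 6-month point.

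**Section 9.2.** Replace the reference to metastatic study arms with Group 2.

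**Section 2.2.** State that any PFS or OS comparison with PD-1 inhibition alone is descriptive and external.

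**Section 7.1.** Delete the mention of randomisation from the ctDNA baseline. Which draw serves as that baseline is a separate scheduling question.

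**Cost.** Wording only. No test that can be run is lost in sections 7.2 and 9.2, and the only rate dropped is one that follow-up cannot supply. Precision with 24 men stays modest, and the intervals will show it.
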